16.0 Health Information and Privacy Compliance

16.1 Select which of the following is applicable to your research:

- My research does not require access to individual health information and therefore assert HIPAA does not apply.
- I am requesting that all research participants sign a HIPCO approved HIPAA Disclosure Authorization to participate in the research (either the standalone form or the combined consent and HIPAA Authorization).
- I am requesting the IRB to approve a Waiver or an alteration of research participant authorization to participate in the research.
- An external IRB (e.g. Advarra) is reviewing and we are requesting use of the authorization language embedded in the template consent form in lieu of the U of M stand-alone HIPAA Authorization. Note: External IRB must be serving as the privacy board for this option.

16.2 Identify the source of Private Health Information you will be using for your research (Check all that apply)

- I will use the Informatics Consulting Services (ICS) available through CTSI (also referred to as the University's Information Exchange (IE) or data shelter) to pull records for me
- I will collect information directly from research participants.
- I will use University services to access and retrieve records from the Bone Marrow Transplant (BMPT) database, also known as the HSCT (Hematopoietic Stem Cell Transplant) database.
- I will pull records directly from EPIC.
- I will retrieve record directly from axiUm / MiPACS
- I will receive data from the Center for Medicare/Medicaid Services
- I will receive a limited data set from another institution
- Other. Describe: Other source of data is from the app which is managed by Smokefree.gov. This data will be identified with a unique participant ID. Thus, only de-identified data will transferred.

16.3 Explain how you will ensure that only records of patients who have agreed to have their information used for research will be reviewed.

NA

16.4 Approximate number of records required for review:

NA

MEDICAL PROTOCOL (HRP-590)

PROTOCOL TITLE: QuitGuide for American Indians: Aims 2 & 3

VERSION DATE: 11-16-2022

16.5 Please describe how you will communicate with research participants during the course of this research. Check all applicable boxes

This research involves record review only. There will be no communication with research participants.

Communication with research participants will take place in the course of treatment, through MyChart, or other similar forms of communication used with patients receiving treatment.

Communication with research participants will take place outside of treatment settings. If this box is selected, please describe the type of communication and how it will be received by participants.

Communication will take place by phone/text, email, and virtually.

16.6 Explain how the research team has legitimate access to patients/potential participants:

All participants will sign a consent form.

16.7 Location(s) of storage, sharing and analysis of research data, including any links to research data (check all that apply).

In the data shelter of the [Information Exchange \(IE\)](#)

Store Analyze Share

In the Bone Marrow Transplant (BMT) database, also known as the HSCT (Hematopoietic Stem Cell Transplant) Database

Store Analyze Share

In REDCap (recap.ahc.umn.edu)

Store Analyze Share

In Qualtrics (qualtrics.umn.edu)

Store Analyze Share

In OnCore (oncore.umn.edu)

Store Analyze Share

In the University's Box Secure Storage (box.umn.edu)

Store Analyze Share

In an AHC-IS supported server. Provide folder path, location of server and IT Support Contact:

cancer.ahc.umn.edu\cancer\CancerCenter\Biostat\CCSG\[name]\R21-AI and NCI
QuitGuide\Data

Store Analyze Share

In an AHC-IS supported desktop or laptop.

Provide UMN device numbers of all devices: 20191709

MEDICAL PROTOCOL (HRP-590)

PROTOCOL TITLE: QuitGuide for American Indians: Aims 2 & 3

VERSION DATE: 11-16-2022

Store Analyze Share

Other. Describe:

Smokefree.gov will maintain de-identified participant app use data. This will be shared with the study team. Also, all de-identified saliva samples will be stored in a locked freezer overseen by the PI in Mayo 11th floor, Division of Environmental Health Sciences until shared with Masonic Cancer Center for analysis.

Indicate if data will be collected, downloaded, accessed, shared or stored using a server, desktop, laptop, external drive or mobile device (including a tablet computer such as an iPad or a smartform (iPhone or Android devices) that you have not already identified in the preceding questions

I will use a server not previously listed to collect/download research data

I will use a desktop or laptop not previously listed

EnHS-M-DCLAP (supported through Environmental health Sciences, School of Public Health); No device number

I will use an external hard drive or USB drive ("flash" or "thumb" drives) not previously listed

I will use a mobile device such as an tablet or smartphone not previously listed

16.8 Consultants. Vendors. Third Parties.

We have a data use agreement with Smokefree.gov for collection and transfer of app user data. Please refer to the data use agreement included.

We will have de-identified audio recordings from the interviews among a subset of the participants transcribed by a third party.

16.9 Links to identifiable data:

All identifiable information will either be paper documents, locked in the PI or project coordinator's office in a locked cabinet, or in a folder on Box separate from study-related data. A link between the identifiable information and study-related data will be saved similarly.

16.10 Sharing of Data with Research Team Members.

All electronic data to be shared with research team will be identified by participant ID and/or app ID. Only those on the IRB or described in the consent form (i.e., Smokefree.gov) will have access to participant data.

16.11 Storage of Documents:

Participant saliva samples and electronic data will be stored until manuscripts are written.

16.12 Disposal of Documents:

We will maintain all consent forms as well as REDCap documents and data transferred from Smokefree.gov for a total of 7 years per the

MEDICAL PROTOCOL (HRP-590)

PROTOCOL TITLE: QuitGuide for American Indians: Aims 2 & 3

VERSION DATE: 11-16-2022

State of Minnesota. After that paper documents will be shredded in paper shredder and REDCap and Smokefree.gov data will be archived/stored indefinitely.

17.0 Confidentiality

17.1 Data Security:

All data is stored in one of the following secure systems: Box, REDCap, locked cabinet, locked freezer or the above mentioned AHC-IS supported biostat server.

18.0 Provisions to Monitor the Data to Ensure the Safety of Participants

18.1 Data Integrity Monitoring.

Oversight for quality control and adherence to protocol procedures will be conducted by [name]. A start-up meeting with the investigative team and the research coordinator will occur prior to participant enrollment. During this meeting, [name] will provide the research coordinator with training on the study protocol, standard operating procedures, equipment and data collection platforms. [name] will closely monitor all procedures to be used in this study. Such monitoring will consist of frequent in-person discussion with the research coordinator to make sure that all protocol procedures are followed, and regular phone meetings to provide updates on study progress and review the data collection process, and other issues of concern.

Data will be collected in a consistent manner either through an interview with the research coordinator or via a REDCap survey that is completed by the participant.

18.2 Data Safety Monitoring.

N/A This study is considered not greater than minimal risk.

19.0 Provisions to Protect the Privacy Interests of Participants

19.1 Protecting Privacy:

The coordinator will first ask the participant if they are in a safe place to complete the interviews and will refuse to conduct any interview if it is known that the participant is in an unsafe location or environment (e.g., driving a vehicle).

All information from the study will be stored in a locked filing cabinet or password protected computer, and only the PI and key study personnel will have access. Participants will not be identified by name in any published report and will be given study specific numbers or false names. Participants will be told their participation will be strictly confidential that any identifying information will only be available to the research team. Participants will be told that tribal leaders and/or clinic leadership will determine if the Tribe/clinic is named or is anonymous in any publication or dissemination of the data.

Each participant will be assigned a unique participant ID. All interview or survey data will be de-identified and coded with their participant ID and stored in REDCap. The participants' returned saliva sample will also be de-identified and coded with the participant ID. The key linking participant names to their participant ID will be stored in password protected BOX folder, and only the PI and key study personnel will have access to this document.

MEDICAL PROTOCOL (HRP-590)

PROTOCOL TITLE: QuitGuide for American Indians: Aims 2 & 3

VERSION DATE: 11-16-2022

An App ID (different from their participant ID) will be entered into the app upon login for the first time. The App ID will also be stored in password protected BOX folder with access only provided to the IRB approved study team. The file in BOX will be the only way to link the app ID and the participant ID together and these IDs with their contact information. Other than dates, no PHI is collected by the app. Data collected from the participant using the GPS function in the app includes no physical locations just that it is a function being utilized by the user.

19.2 Access to Participants:

Participants will sign a consent giving access to the study team.

20.0 Compensation for Research-Related Injury

20.1 Compensation for Research-Related Injury:

The study does not involve greater than minimal risk. However, the consent form includes standard not greater than minimal risk injury language.

20.2 Contract Language:

Not applicable. No contract.

21.0 Consent Process

21.1 Consent Process (when consent will be obtained):

The consenting process will take place at the baseline visit prior to any data collection and randomization. During the consent process, participants will be provided with an opportunity to have their questions and concerns addressed. We will use an electronic informed consent process through REDCap. There is no waiting period necessary between signing consent and collection of data.

21.2 Waiver or Alteration of Consent Process (when consent will not be obtained):

No Waiver or Alteration of the Consent Process will be used for this study.

21.3 Waiver of Written/Signed Documentation of Consent (when written/signed consent will not be obtained):

No Waiver of Written/Signed Documentation of Consent will be used in this study.

21.4 Non-English Speaking Participants:

Participants who cannot speak or read English are excluded from the study because the QuitGuide app is currently only available in English.

21.5 Participants Who Are Not Yet Adults (infants, children, teenagers under 18 years of age):

This study will only enroll adults.

21.6 Cognitively Impaired Adults, or adults with fluctuating or diminished capacity to consent:

Individuals with cognitive impairments or with capacity to consent issues will not be enrolled.

21.7 Adults Unable to Consent:

All participants must be able to consent for themselves.

22.0 Setting

MEDICAL PROTOCOL (HRP-590)

PROTOCOL TITLE: QuitGuide for American Indians: Aims 2 & 3

VERSION DATE: 11-16-2022

22.1 Research Sites:

The community partners include Native American Community Clinic (NACC), the Bad River Band Tribe in Wisconsin, and the American Indian Cancer Foundation (AICAF). See letters of support from NACC, Bad River Tribal leadership, and AICAF

Potential participants will be recruited from NACC and the Bad River Band Tribe communities and their networks. These two partners are to be considered Research Locations only.

AICAF will assist with study procedures and are to be considered a Research Site. All study-related interactions will take place virtually. The interviewer will be in a private room when interacting with the participant virtually. We will ask all interviewees to locate a private room or one that they find suitable for the interview.

Community partners helped develop the protocol. We will engage the communities through a Community Advisory Board (CAB) which includes community members (5-10) and stakeholders who are not participants.

22.2 International Research:

This is not international research.

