of ownership was at 66%, which was among persons of low education.¹⁶ Additionally, a 2018 study reported 86% of AI peoples use a smartphone as their news source.¹⁸ **Finally, apps for Indigenous language preservation and revitalization are being used by Tribes, which suggests that apps are a promising platform for delivery of other content to AI peoples.**¹⁹

For all of these reasons, we are now proposing to test the feasibility and acceptability of a culturally-tailored version of the QuitGuide, developed by our team, versus the standard QuitGuide among American Indian persons in MN and WI.

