9.0 Vulnerable Populations

9.1 Vulnerable Populations:

Population / Group	Identify whether any of the following populations will be focus of the research (targeted), included, but not necessarily the focus or excluded from participation in the study.
Children	Excluded
Pregnant women/fetuses/neonates	included but not the focus
Prisoners	Excluded
Adults lacking capacity to consent and/or adults with diminished capacity to consent, including, but not limited to, those with acute medical conditions, psychiatric disorders, neurologic disorders, developmental disorders, and behavioral disorders	Excluded
Non-English speakers	Excluded
Those unable to read (illiterate)	Excluded
Employees of the researcher	included but not the focus
Students of the researcher	included but not the focus
Undervalued or disenfranchised social group	included but not the focus
Active members of the military (service members), DoD personnel (including civilian employees)	included but not the focus

MEDICAL PROTOCOL (HRP-590)

PROTOCOL TITLE: QuitGuide for American Indians: Aims 2 & 3

VERSION DATE: 11-16-2022

Individual or group that is approached for participation in research during a stressful situation such as emergency room setting, childbirth (labor), etc.	Excluded
Individual or group that is disadvantaged in the distribution of social goods and services such as income, housing, or healthcare.	included but not the focus
Individual or group with a serious health condition for which there are no satisfactory standard treatments.	included but not the focus
Individual or group with a fear of negative consequences for not participating in the research (e.g. institutionalization, deportation, disclosure of stigmatizing behavior).	included but not the focus
Any other circumstance/dynamic that could increase vulnerability to coercion or exploitation that might influence consent to research or decision to continue in research.	included but not the focus

9.2 Additional Safeguards, if any, to ensure inclusion is appropriate:

Individuals representing these vulnerable groups are not targeted for inclusion but may be included if the eligibility criteria is met. While this study is targeting American Indians, a historically disadvantaged population, members of this group should not be assumed to automatically have additional vulnerabilities.

9.3 If research includes potential for direct benefit to participants, provide rationale for any exclusions indicated in the table above:

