15.0 Statistical Considerations

15.1 Data Analysis Plan:

No blinding of the investigative team will occur.

General Approach

All statistical analyses will be performed using SAS (version 9.4) or R (latest version, R Core Team). All statistical tests will be two-sided and a significance level of 0.05 will be used. Proper transformation such as the logarithm transformation will be used to approximate normality for

MEDICAL PROTOCOL (HRP-590)

PROTOCOL TITLE: QuitGuide for American Indians: Aims 2 & 3

VERSION DATE: 11-16-2022

the outcome variables. All analyses will be completed using intent-to-treat principle unless otherwise noted.

Describing the Study Population

Baseline characteristics will be summarized for all participants and by study arm to identify any treatment group imbalances post-randomization. This will include household income, education level, traditional tobacco use, cultural identity, multiple tobacco use, quit readiness, nicotine dependence and CPD. Continuous variables will be summarized using mean, standard deviation, median and range, and compared between study arms using Student's t-tests or Wilcoxon rank-sum tests, as appropriate. Categorical variables will be summarized using frequency and percentage, and compared between study arms using Chi-square or Fisher's exact tests, as appropriate.

Primary Endpoint Analysis

The primary endpoint is the frequency of app use initiated by the participant. The number of times the app is initiated per day will be measured using data from Smokefree.gov. If a participant does not use the app on a particular day, Smokefree.gov records this as non-use or 0 for that day. The total number of times will be summarized for analysis by totaling the number of times the app is initiated from randomization to 5 weeks post-randomization.

Primary Analysis

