25.0 Resources Available**25.1 Resources Available:**

We foresee the recruitment to be feasible based on previous studies within this population and with the same community partners.

This project is funded by the NCI and has sufficient funding to be accomplished. Any additional, unforeseen, funding required will be covered by [name].

[name], the PI, has sufficient resources to oversee this project and conduct human subjects procedures.

The American Indian Cancer Foundation staff will assist with the human subjects components. If any individual from the community partners, who does not have their own IRB, is involved in any human subjects research, this individual will complete appropriate training (CITI through UMN) and be added to the IRB submission as study staff.

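### Employees and students of the team that developed the tailored app may enrol, and the plan neither excludes nor identifies participants with a stake in it

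*Combined protocol and SAP*

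**What the plan says.** **Who may enrol.** The table in Section 9.1 has rows for "Employees of the researcher" and "Students of the researcher". Both carry the entry that admits a group without targeting it. Section 9.2 gives the only safeguard: "Individuals representing these vulnerable groups are not targeted for inclusion but may be included if the eligibility criteria is met". The exclusions in Section 8.2 are a recent start or change of cessation pharmacotherapy, and not speaking or reading English. Neither concerns a link to the study.

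**Who has a stake.** Section 2.3 says the trial tests "a culturally-tailored version of the QuitGuide, developed by our team". AICAF is a subcontractor (Section 2.3) and a research site (Section 22.1), and Section 25.1 adds: "The American Indian Cancer Foundation staff will assist with the human subjects components". Section 22.1 says the communities are engaged through a "Community Advisory Board (CAB) which includes community members (5-10) and stakeholders who are not participants".

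**What is measured.** The primary endpoint is the number of participant-initiated app launches over 5 weeks, taken from Smokefree.gov data (Sections 3.1 and 15.1). Usability, acceptability and cultural fit are self-rated at the exit survey (Section 3.2).

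**Masking and analysis.** On masking, Section 15.1 says only this: "No blinding of the investigative team will occur". The primary analysis uses everyone randomised. The one sensitivity analysis of the primary endpoint is restricted to those who complete the week 5 survey.

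**The concern.** Call an insider anyone who is an employee or student of the study team, works on the study, or sits on the advisory board. Such a person probably knows that a tailored version exists and that the team hopes it does better. The standard app is public and the tailored one is not (Section 4.1), so an insider could probably tell which one had been assigned. Section 19.1 leaves the key that links names to participant IDs with the PI and key personnel. An employee or student would therefore be rating an employer's or teacher's product in a form that can be traced.

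Randomisation equalises the expected number of insiders per arm. It does not remove a preference that raises scores in the tailored arm and lowers them in the standard arm, because the two effects add in the arm difference. The self-rated endpoints are the most exposed. Launches are logged and cannot be misreported, but an insider can still open the app more or less often. The measures listed in Section 5.2 include no affiliation item, so the analyst could not examine the question afterwards.

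**Working it through.** **1. The plan's own figure.** Section 15.2 gives 58 per arm for 80% power to detect 35 versus 38.15 launches, two-sided alpha 0.05. For two Poisson rates, n per arm = (1.960 + 0.842)² × (35 + 38.15) / 3.15² = 57.9, rounded up to 58. The figure reproduces, and nothing below changes it.

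**2. Inputs for the ratings.** From the documents: 58 per arm, two-sided 5%. Assumed, because the documents do not give them: a 5-point rating with SD 1, k insiders per arm, and a shift of s points by each insider, up in the tailored arm and down in the standard arm.

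- SE of the arm difference = √(2/58) = 0.186.
- Bias in the difference = 2ks/58.
- z = bias / SE.
- Two-sided false-positive rate = Φ(−1.96 + z) + Φ(−1.96 − z).

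For s = 1:

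| k per arm | bias | z | false-positive rate |
|---|---|---|---|
| 1 | 2/58 = 0.034 | 0.19 | 5.4% |
| 2 | 4/58 = 0.069 | 0.37 | 6.6% |
| 3 | 6/58 = 0.103 | 0.56 | 8.6% |

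**3. Range.** If only tailored-arm insiders shift, by 1 point, the bias is k/58 and the rates for k = 1, 2, 3 are about 5.1%, 5.4% and 5.9%. If insiders in both arms shift by 2 points, the rates are 6.6%, 11.5% and 20%. The last needs six insiders in all (6/116 = 5% of the trial), each moving 2 SD.

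**4. Launches.** Assume k insiders in the tailored arm each open the app 35 extra times over 5 weeks, with no change in the standard arm. The bias is 35k/58 = 0.60, 1.21 or 1.81 launches for k = 1, 2, 3, which is 19%, 38% or 57% of the planned 3.15. Under the pure Poisson variance of Section 15.2, the false-positive rates are about 8.5%, 19% and 37%. If the SD is about 35 instead (over-dispersed counts, for which Section 15.1 provides a negative binomial fallback), they are about 5.1%, 5.4% and 5.9%. The result depends almost entirely on a variance that the documents do not give.

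**5. How many insiders?** The documents give no number. Under Section 8.1 an insider must also self-report as American Indian, smoke at least 3 cigarettes a day and want to quit. Under 8.2 they must have had no new or changed cessation pharmacotherapy in the past month. That points to few, and zero is possible.

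**The case against.** The strongest reply is that Section 9.1 is a vulnerability table. It asks whether groups open to coercion are targeted, admitted or excluded, and gives staff and students the same entry as pregnant women and service members. Nothing suggests that they are being recruited, and narrow eligibility may leave none. This limits the size of the problem. It does not change the rule, which admits people with a stake and provides no check.

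A second reply is that cultural content is visible to anyone using the tailored app, so reaction to allocation is a question for all 116 participants and removing a few insiders would not settle it. That is right as far as it goes. Insiders differ in having a stake in the result, and they are the part that an eligibility line can remove.

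A third is that a broad exclusion would do harm. Barring everyone who helped develop the app could catch Aim 1 participants, whom Section 11.1 names as a recruitment source; the documents do not say whether they contributed to the tailoring. Barring all partner staff could remove ordinary employees in the communities from which Section 22.1 recruits. This stands, and the fix is drawn narrowly for that reason.

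A reader might also infer three stronger things:

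- **That Section 22.1 contradicts Section 9.1 by keeping the board out of the trial.** It does not. The sentence describes community engagement, its closing words may qualify only the stakeholders, and Section 8.2 has no matching rule.
- **That participants are known to be unblinded.** The protocol speaks only of the investigative team and is silent on participants. That insiders would recognise their arm is a plausible inference, not a stated fact.
- **That the error rate is seriously inflated.** The 20% figure needs six insiders each moving 2 SD. On a 5-point item, equal 2-point moves up and down from a common honest rating fit the scale only if that rating is exactly 3.

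**Conclusion.** The concern holds as a minor, avoidable weakness in eligibility. The rule in 9.1 admits people connected to the team that developed one of the two apps, 8.2 does not stop them or other study personnel, and the plan could neither detect nor test their influence. On a rating, one to three insiders per arm with a 1-point shift in each arm would move the false-positive rate from 5% to about 5.4–8.6%. That rests on an assumed SD of 1, an assumed reaction and an unknown count that may be zero. For launches, the effect could be material under pure Poisson variance and negligible under marked over-dispersion. The sample size and the analysis model are unaffected.

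**What to change.** - In Section 9.1, change the employee and student rows to excluded.
- In Section 8.2, add: *employee or student of the study team, personnel working on this study at UMN, AICAF or a partner, or advisory-board member*.
- Add one matching question to the telephone screener.
- Keep ordinary employees of partner communities and Aim 1 participants eligible. Record prior Aim 1 participation and repeat the analyses without those people as a sensitivity check.

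The cost is one exclusion line, two table entries, one screener question, one recorded item and one additional sensitivity analysis. A few otherwise eligible people could not enrol. The target of 116 does not change.
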